Type 2 Diabetic subjects	18-70 yrs old BMI = 25-45 kg/m ² HbA1C < 10% Other than diabetes, subjects must be in good general health as determined by physical exam, medical history, blood chemistries, CBC, TSH, T4, EKG and urinalysis Only subjects whose body weight has been stable (\pm 3 lbs) over the preceding three months and who do not participate in an excessively heavy exercise program will be included.	Subjects taking drug known to affect glucose metabolism (other than metformin and sulfonylurea) Individuals with evidence of proliferative diabetic retinopathy, plasma creatinine >1.4 females or >1.5 males, or 24-hour urine albumin excretion > 300 mg will be excluded.

Item 6

Research Plan / Description of the Research Methods a. *Provide a comprehensive narrative describing the research methods. Provide the plan for data analysis (include as applicable the sample size calculation).*

Step-by-Step Methods: Screening Visit. Medical history is obtained and physical exam performed. Blood is drawn for FPG, blood chemistries, lipid profile, HbA1c, and thyroid function. Urine analysis, EKG and pregnancy test are performed.

Study 1: Effect of Dapagliflozin on EGP: EGP will be measured with 3-³H-glucose infusion. The 3-³H-glucose infusion will be started at 6 AM and arterialized blood samples will be drawn from a catheter placed retrogradely in a vein on the dorsum of the hand to measure the basal rate of EGP. The hand will be placed in a box heated to 70°C to ensure arterialization of the venous blood. After a 3 hour tracer equilibration period (at 9 AM) subjects will receive dapagliflozin (10 mg) or placebo, and blood samples will be drawn every 10-20 minutes for 5 hours (until 2 PM) for the measurement of plasma glucose, insulin, C-peptide, glucagon, cortisol, catecholamine concentrations and [3-³H]-glucose specific activity. Urine will be collected from 6 to 9 AM and from 9 AM to 2 PM. Urinary volume and glucose conc will be measured and the rate of urinary glucose excretion quantitated. The study will end at 2 PM and subjects will be allowed to return home. Basic metabolic panel will be performed during the study to monitor renal function.

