Study 2: Effect of Dapagliflozin on EGP With Glucose Clamp: EGP will be measured with 3-³H-glucose infusion as described in Study 1 above. The 3-³H-glucose infusion will be started at 6 AM to measure the basal rate of EGP. After a 3 hour tracer equilibration period (at 9 AM) subjects will receive dapagliflozin (10 mg) or placebo, and the plasma glucose conc will be measured every 5 minutes for 5 hours (from 9AM to 2 PM). A variable infusion of 20% dextrose will be adjusted to clamp the plasma glucose conc at the fasting level (+5%) until the end of the study (2 PM). Blood samples will be drawn every 10-20 minutes for 5 hours (2 PM) for the measurement of plasma glucose, insulin, C-peptide, glucagon, cortisol, catecholamine concentrations and [3-³H]-glucose specific activity. Urine will be collected from 6 to 9 AM and from 9 AM to 2 PM. Urinary volume and glucose concentration will be measured and the rate of urinary glucose excretion quantitated. The study will end at 2 PM and subjects will be allowed to return home. Basic metabolic panel will be performed during the study to monitor renal function.

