Study 3: Effect of Dapagliflozin on EGP with Pancreatic Clamp: In this study, EGP will be measured as described in Study 1 above and plasma insulin and glucagon concentrations will be clamped at the basal level using the pancreatic clamp technique, while the plasma glucose concentration will be allowed to decrease spontaneously after dapagliflozin and placebo administration. Somatostatin (750 µg/h) infusion will be started at 5:45 AM (15 minutes before the start of [3-³H]-glucose infusion [6 AM]) along with basal infusions of glucagon (0.3 ng/kg.min) and insulin (0.1 mU/kg.min) to replace basal plasma glucagon and insulin concentrations. The somatostatin, glucagon and insulin infusions will be continued for the entire duration of the study (until 2 PM). At 6 AM a prime (0.4 uCi x FPG) – continuous (0.4 uCi/min) infusion of [3-³H]-glucose will be started and continued to 2 PM. At 9AM, subjects will ingest dapagliflozin (10 mg) or placebo (2:1 randomization ratio) and blood samples will be drawn at -30, -20, -10, 5 and 0 minutes before and every 10-20 minutes after drug administration (until 2 PM) for the measurement of plasma glucose, insulin, C-peptide, glucagon, cortisol, catecholamine concentrations, and plasma [3-³H]-glucose specific activity. Urine will be collected from 6 to 9 AM and from 9 AM to 2 PM. Urinary volume and glucose concentration will be measured and the rate of urinary glucose excretion will be calculated. The study will end at 2 PM. Basic metabolic panel will be performed during the study to monitor renal function.

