Data Analysis Plan: Data Analysis and Statistical Methods: Under steady-state postabsorptive conditions, the basal rate of endogenous glucose appearance ($R_a = bEGP$) equals the 3-³H-glucose infusion rate divided by steady state plasma tritiated glucose specific activity. After drug administration, non-steady conditions for 3-³H-glucose specific activity prevail and the rate of whole body glucose appearance (R_a) is calculated from Steele's equation. During the glucose clamp study, the rate of EGP after drug administration equals R_a minus glucose infusion rate, while, during the pancreatic clamp, $R_a = EGP$ since no cold glucose is infused. The difference in EGP during the last hour of the study (240-300 minute) between subjects receiving dapagliflozin and subjects receiving placebo represents the increase in EGP caused by dapagliflozin (glucosuria-stimulated increase in EGP). The glucosuria-stimulated increase in EGP will be compared among the three studies with ANOVA. Post hoc testing will be performed with a Bonferroni correction for multiple comparisons. The difference in glucosuria-stimulated increase in EGP between study 2 and study 1 represents the contribution

of the decrease in plasma glucose conc to the increase in EGP, while the difference between study 3 and study 1 represents the contribution of change in islet hormones (insulin/glucagon) to the increase in EGP.

Item 7 Risks Section:

Complete the following table to describe the risks of all **research procedures** listed in Step 2, Institutional Form (items 28-34). *Do not list risks of Routine care procedures here.*

N/A, Risks are described in the informed consent document – do not complete this table.

Research procedures	Risks
example: 
• History and physical• Questionnaire• Laboratory tests	List the reasonably expected risks under the following categories as appropriate:
Add or delete rows as needed	

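### Basal EGP is measured before dosing on every study day but is not used in estimating the drug effects; adjusting for it would be an optional gain in precision within each study

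*Combined protocol and SAP*

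**What the plan says.** Item 2 randomises 30 subjects 2:1, 20 to dapagliflozin and 10 to placebo. Each subject has three study days within one to two weeks.

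Item 6 obtains basal EGP before the 9 AM dose each time:

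- **Study 1:** the tracer starts at 6 AM, with blood taken from a catheter "in a vein on the dorsum of the hand to measure the basal rate of EGP".
- **Study 2:** the tracer "glucose infusion will be started at 6 AM to measure the basal rate of EGP".
- **Study 3:** "EGP will be measured as described in Study 1 above and plasma insulin and glucagon concentrations will be clamped at the basal level". The somatostatin "infusion will be started at 5:45 AM (15 minutes before the start of" the tracer, and "blood samples will be drawn at -30, -20, -10, 5 and 0 minutes before and every 10-20 minutes after drug administration". The pre-dose value here is therefore taken with the pancreatic clamp already running.

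The analysis text starts from "Under steady-state postabsorptive conditions, the basal rate of endogenous glucose appearance", defined as tracer infusion rate over steady-state specific activity. It then defines the drug effect in each study as "The difference in EGP during the last hour of the study (240-300 minute) between subjects receiving dapagliflozin and subjects receiving placebo". After that, "The glucosuria-stimulated increase in EGP will be compared among the three studies with ANOVA", with Bonferroni-corrected post hoc tests. The Study 2 vs 1 and Study 3 vs 1 differences are read as the contributions of falling glucose and of islet hormones. No covariate, change from basal or ANCOVA is named.

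**The concern.** A pre-dose measurement of the outcome itself is often its best predictor. With arms of 20 and 10, the chance difference between arms in mean basal EGP has a standard deviation of √(1/20 + 1/10) = 0.39 SD. The raw last-hour difference leaves any such imbalance in the estimate. In a trial of 30 subjects the lost precision could matter.

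The plan is also silent on the role of basal EGP, although Item 2 justifies the five-hour measurement by a rise over baseline. An analyst could choose between raw, change-from-basal and adjusted estimates after seeing the data.

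**Working it through.** **1. Inputs.** Arm sizes are 20 and 10 (Item 2): 30 × 2/3 = 20 and 30 × 1/3 = 10, as stated. The documents give no SD, effect size, power or correlation, so there is no design calculation to reproduce. Every correlation below is an assumption.

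**2. Within-study effect.** With last-hour SD σ and correlation r between basal and last-hour EGP:

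- Raw difference: variance = σ²(1/20 + 1/10) = 0.15σ².
- ANCOVA with one covariate: variance = 0.15σ²(1 − r²)(N − 3)/(N − 4). The last factor is 27/26 = 1.038.
- Break-even: (1 − r²)(27/26) = 1, so r = √(1/27) = 0.192.

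| Assumed r | ANCOVA/raw variance | Equivalent unadjusted N (30/ratio) |
|---|---|---|
| 0 | 1.038 | 28.9 |
| 0.3 | 0.945 | 31.7 |
| 0.5 | 0.779 | 38.5 |
| 0.7 | 0.530 | 56.6 |
| 0.8 | 0.374 | 80.2 |

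A simulation (200,000 trials per correlation) gave ratios of 1.038, 0.780 and 0.530 at r = 0, 0.5 and 0.7. Both estimators were within 0.0015 SD of the true value on average. Comparing 95% confidence interval widths moves the break-even only to 0.20. With 27 or 24 completers (assumed) it is 0.20 or 0.22.

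An unadjusted change score is not an equivalent remedy. With equal SDs its variance ratio is 2(1 − r), which beats the raw difference only when r exceeds 0.5.

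**3. Between-study contrasts.** If each subject keeps one arm on all days, as Item 2 reads, the contrast rests on each subject's difference between two days. Stable subject differences cancel, so only the within-subject correlation r_w can help.

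- Regressing the between-day difference on arm and each day's basal EGP (two covariates) gives a ratio of (1 − r_w²)(N − 3)/(N − 5) = (1 − r_w²)(27/25). This is 1.08, 1.04, 0.81 and 0.55 at r_w = 0, 0.2, 0.5 and 0.7. Simulation (40,000 runs) agrees.
- If basal EGP predicts within subject in Study 1 but not under the Study 3 clamp, the simulated Study 3 vs 1 ratio is 0.99–1.01 at Study 1 r_w = 0.5 and 0.90–0.93 at 0.7.
- Subtracting separately fitted ANCOVA estimates gives 1.22–1.59 at r_w = 0 and 1.09–1.34 at 0.2. This assumes a between-subject variance share of 0.5 or 0.8 and a between-subject correlation of 0.8 or 0.9. With a share of 0.5 and a correlation of 0.3 it is 1.09 at r_w = 0, so the size of the penalty depends on these assumptions.

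**4. Carry-over.** No minimum gap between days is stated. Suppose an earlier dose shifts later-day basal EGP by b and last-hour EGP by c in the dapagliflozin arm. The raw contrast, and one adjusted only for first-day basal EGP, shift by c. The contrast adjusted for each day's basal EGP shifts by c − r_w·b. At r_w = 0.5/0.7:

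| Scenario (SD units) | Raw or first-day-basal | Adjusted for each day's basal |
|---|---|---|
| b = 0.3, c = 0 | 0 | −0.15 / −0.21 |
| b = 0.3, c = 0.3 | +0.30 | +0.15 / +0.09 |

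Simulation agrees to within about 0.01. The ranking of the estimators reverses between the two scenarios.

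**The case against.** The case for leaving the plan alone is strong. The raw difference is valid and simple. Nothing in the documents places r above 0.19. The mechanistic conclusions come from the between-study contrasts, which should stay primarily unadjusted in any case. At present the three effects subtract, with complete data, to the stated contributions; ANCOVA effects would not do so exactly. All of this stands, and it is why the point is minor. It does not remove the case for saying how basal EGP will be used, since the data are collected anyway and the expected loss is small.

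A reader might infer three stronger points, none of which the documents support:

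- **That the planned estimate is biased.** Under the stated randomisation it is not; a chance imbalance in one trial is imprecision.
- **That adjustment would sharpen the mechanistic contrasts.** Differencing within subject already removes what is stable, and Study 3 basal EGP is measured under a different hormonal condition.
- **That adjusting only for first-day basal EGP protects against carry-over.** It does so only if carry-over touches basal EGP and spares last-hour EGP. If both shift, it is as biased as the raw contrast and more biased than the one adjusted for each day's basal EGP.

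**Conclusion.** The point holds as a modest matter of precision. Basal EGP is obtained on all three days and then left out of the drug-effect estimates. ANCOVA would be more precise within each study if r exceeds 0.19. Over assumed r from 0.3 to 0.8 the variance falls by about 5% to 63%; at r = 0 it rises by about 4%. The calculation assumes randomisation, complete data and roughly normal values with a linear relation.

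For the Study 2 vs 1 and Study 3 vs 1 contrasts the gain is uncertain and can be nil, provided each subject keeps one arm. The validity of the planned analysis is not in question. Severity is low: an optional improvement.

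**What to change.** In Item 6, data analysis:

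- State that each study's drug effect is estimated by ANCOVA of 240–300 minute EGP on that day's pre-dose basal EGP, fitted separately by study. Use one common pre-dose window; Study 3 lists pre-dose sampling times, while Studies 1 and 2 list none.
- Report the unadjusted difference alongside.
- Keep the between-study contrasts primarily as unadjusted within-subject comparisons, and do not form them by subtracting the separate ANCOVA estimates. A contrast adjusted for each day's basal EGP may be a pre-specified secondary analysis.
- Report basal EGP by arm and study day. Say that, if an earlier dose affects later days, either the adjusted or the unadjusted estimate can be the more biased. Do not present first-day-basal adjustment as a safeguard.

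The cost is a few lines of text and no new data. If basal EGP is not predictive, variance rises by about 4% in the within-study effects and about 8% in the secondary contrast (27/25 = 1.08). The plan should also say that the ANCOVA effects will not subtract exactly to the reported contrasts.

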COVER PAGE FOR PROTOCOL AND STATISTICAL ANALYSIS PLAN

Official Study Title: SGLT2 Inhibition and Stimulation of Endogenous Glucose Production:
Protocol 2

NCT number: NCT02592421

IRB Approval Date: 09/06/2017

Protocol Template Form

Item 1 UTHSCSA Tracking Number	HSC20150668H
-----------------------------------	--------------

Item 2 Abstract / Project Summary	
Provide a succinct and accurate description of the proposed research. State the purpose/aims. Describe concisely the research design and methods for achieving the stated goals. This section should be understandable to all members of the IRB, scientific and non-scientific.
 
DO NOT EXCEED THE SPACE PROVIDED.

------------------------------------------	---------------------------------------------------------------------------------------------------------------------------------------------------------------------------------------------------------------------------------------------------------------------------------------------------------------------------------------------------------------------

Purpose/Objectives: We will determine the role of pancreatic hormones (increase in plasma glucagon and decrease in plasma insulin concentration) in the stimulation of EGP following SGLT2 inhibition.

Research Design/Plan: After screening, eligible subjects will receive three 5-hour measurements of EGP with administration of study drug after a 3-hour tracer equilibration period. HGP will be measured for 5 hours after drug administration to allow sufficient time for a significant increase in HGP above baseline after dapagliflozin administration (10). In study 1, HGP will be measured for 5 hours after dapagliflozin (10 mg) or placebo administration. Study 2 will be performed under glucose clamp conditions (i.e. maintaining the plasma glucose concentration stable at each subject's fasting level), and Study 3 will be performed under pancreatic clamp conditions (maintaining the plasma glucagon and insulin concentrations constant at the basal level). Subjects will be randomized in a 2:1 ratio; 20 subjects will receive dapagliflozin and 10 subjects will receive placebo. Each study will be performed on a separate day, after a 10-12 hour overnight fast within 1-2 week period.

Methods: Screening visit; Study 1 EGP, Study 2 EGP with Glucose Clamp, Study 3 EGP Pancreatic Clamp

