Item 3 Background 
Describe past experimental and/or clinical findings leading to the formulation of your study.
 
For research involving unapproved drugs, describe animal and human studies.
 
For research that involves approved drugs or devices, describe the FDA approved uses of this drug/device in relation to your protocol.
	
Insert background: EGP is key to understanding normal glucose homeostasis and development of hyperglycemia in T2DM. We and others have demonstrated that glucosuria produced by SGLT2 inhibition stimulates an increase in EGP, suggesting the presence of a strong interaction between the kidney and liver, i.e. "a reno-hepatic axis" that coordinates the regulation of EGP and plasma glucose concentration. The present study will provide evidence for the presence of this previously unrecognized reno-hepatic axis and define the mechanisms which underlie the interaction between the kidney and liver. In addition to providing novel insights concerning the regulation of glucose homeostasis, the present study has direct and important clinical implications. Although SGLT2 inhibitors are effective in producing glucosuria, they cause only a modest decrease in HbA1c (0.6-0.8%). On one hand, the presence of a "reno-hepatic axis" that leads to a compensatory increase in EGP in response to glucosuria maintains the FPG within the normal range in NGT individuals and prevents hypoglycemia. On the other hand, the increase in EGP in T2DM individuals is "paradoxical" in that it occurs while the plasma glucose concentration is within the hyperglycemic range and quantitatively offsets by ~50% urinary glucose loss (see results below) produced by SGLT2 inhibitors and markedly attenuates their glucose lowering effect. Thus, determining the mechanisms that mediate the rise in EGP in response to glucosuria will allow the development of strategies that prevent the rise in EGP and increase the efficacy of SGLT2 inhibitors. Our preliminary data suggest an important role for increased glucagon secretion in mediating the "reno-haptic" interaction. In the present study, we will examine whether co-administration of the GLP-1 receptor agonist liraglutide with the SGLT2 inhibitor (dapagliflozin) can prevent the compensatory increase in EGP in response to

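### Study 2 minus Study 1 is the net effect of preventing the glucose fall, possibly with more glucosuria; the plan reads it all as the glucose contribution and leaves the urinary glucose it collects unused

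*Combined protocol and SAP*

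**What the plan says.** The Data Analysis Plan in Item 6 takes EGP over the last hour, dapagliflozin minus placebo, and states that this difference "represents the increase in EGP caused by dapagliflozin (glucosuria-stimulated increase in EGP". It compares that quantity among the three studies by ANOVA with Bonferroni-corrected post hoc tests. The difference between Study 2 and Study 1 is read as the contribution "of the decrease in plasma glucose conc to the increase in EGP"; the difference between Study 3 and Study 1 is read as the islet-hormone contribution.

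The studies handle plasma glucose differently after dosing. In Study 2, "A variable infusion of 20% dextrose will be adjusted to clamp the plasma glucose conc at the fasting level" until the end of the study. In Study 3, "the plasma glucose concentration will be allowed to decrease spontaneously after dapagliflozin and placebo administration". Study 1 has no clamp, and the reading of the Study 2 contrast presupposes that glucose falls there.

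Urine is collected from 6 to 9 AM and from 9 AM to 2 PM in all three studies, and urinary glucose excretion is quantified each time. The Data Analysis Plan does not mention it. The Background (Item 3) treats glucosuria as the stimulus and says that the EGP rise in type 2 diabetes "quantitatively offsets by ~50% urinary glucose loss".

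**The concern.** If glucosuria is the stimulus, comparing the EGP response across studies as a test of mechanism assumes that the stimulus is about the same size in each. Holding glucose at fasting keeps the filtered load above what it would be if glucose fell. With reabsorption inhibited, that could mean more glucosuria in Study 2 than in Study 1.

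Study 2 would then change two things. It removes the glucose fall, which lowers the EGP rise if the fall matters, and it may enlarge the stimulus, which raises it. The plan assigns the net difference to the first alone. A small or null Study 2 minus Study 1 difference could reflect two effects cancelling, yet be reported as showing that falling glucose plays no part. The measurement that would help to tell these apart is collected but has no role in the analysis.

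**Working it through.** **What can be reproduced.** The documents give no SD, effect size, alpha, expected glucose fall or expected urinary glucose by study, so there is no planned figure to reproduce for this contrast. Only the allocation can be checked: "Subjects will be randomized in a 2:1 ratio; 20 subjects will receive dapagliflozin and 10 subjects will receive placebo", and 30 × 2/3 = 20, 30 × 1/3 = 10.

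**Inputs from the documents.** Glucose is clamped in Study 2 and unclamped in Study 1; EGP is read at 240-300 minutes; post-dose urine is one 5-hour pool; the EGP rise is about 50% of urinary glucose loss.

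**Assumptions, none from the documents.**
- Fasting glucose F is 120 to 200 mg/dL.
- Glucose falls linearly in Study 1 by d = 5 to 30 mg/dL at 300 minutes.
- Glucosuria on drug = GFR × (plasma glucose − T), with GFR 1.0 dL/min and T = 0 or 40 mg/dL. Placebo glucosuria is ignored.
- The EGP rise not due to the glucose fall is proportional to glucosuria.

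**Stimulus ratio, Study 2 over Study 1.** A linear fall averages 0.9d over the last hour and d/2 over five hours.
- Last hour: R = (F − T)/(F − 0.9d − T)
- Five-hour pool: R5 = (F − T)/(F − d/2 − T)

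| F | d | T | R |
|---|---|---|---|
| 200 | 5 | 0 | 200/195.5 = 1.023 |
| 160 | 20 | 0 | 160/142 = 1.127 |
| 160 | 20 | 40 | 120/102 = 1.176 |
| 120 | 30 | 0 | 120/93 = 1.290 |
| 120 | 30 | 40 | 80/53 = 1.509 |

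The Study 2 stimulus is thus about 2% to 50% larger. For a fall of only 5 mg/dL it is 2% to 6% larger. At F = 160 and d = 20, the extra urinary glucose in the last hour is 0.9 × 20 × 1.0 = 18 mg/min, or 9 mg/min of EGP at the 50% link. This takes all filtered glucose above T as excreted, so it is an upper figure.

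**Effect on the contrast.** Let m be the true share of the Study 1 EGP rise due to the glucose fall. Set the Study 1 rise to 1; the Study 2 rise is (1 − m)R, and the planned contrast returns an apparent share of 1 − (1 − m)R. At F = 160, d = 20:
- m = 0.25: 1 − 0.75 × 1.127 = 0.155 (T = 0); 1 − 0.75 × 1.176 = 0.118 (T = 40).
- m = 0: −0.127 and −0.176.
- Across the whole range, m = 0.25 reads as anything from 0.233 (R = 1.023) to −0.132 (R = 1.509).

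**Direction.** The model scales the whole remainder with glucosuria. If the clamp also blunts the glucagon rise or insulin fall, multiply the remainder by h < 1, giving an apparent share of 1 − (1 − m)Rh. The two effects cancel at h = 1/R, which is 0.887 for R = 1.127 and 0.850 for R = 1.176. Blunting of more than 11% to 15% would reverse the direction.

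**How far pooled urine corrects it.** Dividing by 5-hour urinary glucose replaces R by R/R5. At F = 160, d = 20, T = 0: R5 = 160/150 = 1.067, R/R5 = 1.056, and m = 0.25 reads as 1 − 0.75 × 1.056 = 0.208. The error falls from 9.5 to 4.2 points, so a little over half is removed.

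**The case against.** The strongest reply is about the estimand. The intervention in Study 2 is preventing the glucose fall, and any extra glucosuria is a consequence of it. On that view the planned contrast is a valid net effect, and what the working calls error is the gap between a total effect and a direct effect at fixed glucosuria. This stands as a defence of the contrast. It does not rescue the interpretation, because the plan does not call it a net effect; it uses the contrast to apportion the EGP rise between mechanisms.

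The second reply is that size and sign rest on assumptions. This also stands. The 50% figure is one aggregate offset and does not show that the EGP rise scales with glucosuria within a subject. A reader might infer that Study 2 glucosuria is known to be higher and that the contrast is biased in one direction, so that a glucose mechanism will be missed. The documents do not support that: higher glucosuria is inferred from filtered load, it could be only about 2% higher, and hormone blunting under the clamp would push the other way.

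The third reply is that the abstract (Item 2) states the purpose as the role of pancreatic hormones, which rests on Study 3 versus Study 1, where glucose is unclamped in both. A reader might extend the concern to that contrast. The stimulus could differ there if glucose fell by different amounts, but nothing in the documents shows that it does.

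**Conclusion.** The concern holds as a limit on interpretation. The randomised comparison within each study is sound, and Study 2 minus Study 1 validly estimates the net effect of preventing the glucose fall. What the plan cannot support is reading all of that difference as the glucose contribution when the clamp may also change the stimulus and the measured urinary glucose is not examined.

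The size is illustrative only: a stimulus about 2% to 50% larger in Study 2, and at the central assumed inputs a true 25% share read as 11.8% to 15.5%. These figures depend on the assumed glucose fall, on glucosuria following filtered load, and on the EGP rise being proportional to glucosuria. The net direction is not certain, and without an SD the possible distortion cannot be set against the trial's precision. The islet-hormone contrast is not shown to be affected.

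**What to change.** Keep the planned contrasts as primary, and change the Data Analysis Plan as follows.

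1. Pre-specify a drug-by-study comparison of urinary glucose excretion from 9 AM to 2 PM. Each subject undergoes all three studies, so the study comparison can be made within subject.
2. Describe Study 2 minus Study 1 as the net effect of preventing the fall in plasma glucose. State that a null or small difference will not be read as absence of a glucose mechanism if urinary glucose is higher in Study 2.
3. Optionally, report the dapagliflozin-minus-placebo EGP rise per unit of dapagliflozin-minus-placebo urinary glucose excretion, by study, as a sensitivity analysis with a subject-level bootstrap interval for the between-study difference.

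Attribution should not be made conditional on the scaled and unscaled contrasts agreeing. Agreement would need a definition, and the two differ by construction whenever the stimulus differs, so such a rule could block a correct attribution in the very case it is meant for.

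The cost is a few lines of text and analysis on data already collected. The downside is that urinary glucose is a post-dose variable from a single 5-hour pool, while EGP is read in the last hour. Scaling therefore corrects only part of any distortion and must remain supportive.

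### The planned ANOVA compares a drug-minus-placebo difference that no subject has, and does not state the drug-by-study term or the subject error term that the question needs

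*Combined protocol and SAP*

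**What the plan says.** Item 2 (Research Design/Plan) sets out the layout. On measurement: "eligible subjects will receive three 5-hour measurements of EGP". On allocation: "Subjects will be randomized in a 2:1 ratio; 20 subjects will receive dapagliflozin and 10 subjects will receive placebo". Drug is therefore a between-subject factor and study a within-subject factor.

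Item 6 (Data Analysis and Statistical Methods) holds the whole analysis plan. It first defines the quantity to be analysed, which is a comparison of two groups of people: "The difference in EGP during the last hour of the study (240-300 minute) between subjects receiving dapagliflozin and subjects receiving placebo". The plan takes this group difference as the effect of the drug and gives it the name used in the later test. It then gives the test: "The glucosuria-stimulated increase in EGP will be compared among the three studies with ANOVA". Multiplicity follows: "Post hoc testing will be performed with a Bonferroni correction for multiple comparisons". The number of comparisons is not given.

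Two contrasts carry the interpretation. The first begins "The difference in glucosuria-stimulated increase in EGP between study 2 and study 1 represents the contribution" and concerns the fall in plasma glucose. The second, Study 3 against Study 1, is read as the share due to islet hormones. Neither document section gives the factors of the ANOVA, a drug-by-study term, a repeated-measures or subject term, an error term or an alpha level.

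**The concern.** An ANOVA needs replicate values of its outcome. The outcome here is a difference between two groups of different people, so each study yields one value and there is nothing to estimate error from. Whoever runs the analysis must turn the sentence into something computable, and the choice fixes the standard error.

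This bears on the trial's stated purpose, because the role of the pancreatic hormones is to be read from the Study 3 against Study 1 contrast. If the placebo mean is subtracted from each dapagliflozin subject, the uncertainty in a mean of only 10 people drops out and a mechanism can be declared too easily. If all 90 values are treated as independent, the pairing within subjects is thrown away and a real mechanism can be missed. The choice should be settled before the data are seen.

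**Working it through.** **Inputs from the documents.** 20 dapagliflozin and 10 placebo subjects, three studies each (Item 2); outcome is EGP at 240–300 minutes (Item 6). The documents give no alpha, SD, correlation or sample-size calculation, so there is no stated figure to reproduce.

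**Assumptions.** Two-sided 5%; common SD σ; within-subject correlation ρ of 0, 0.5 or 0.8; complete data; one assignment per subject; no true drug-by-study effect.

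**Step 1: the literal reading.** Let d1, d2, d3 be the dapagliflozin mean minus the placebo mean in each study. Three values give 2 degrees of freedom between studies and 2 in total, leaving 2 − 2 = 0 for error.

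**Step 2: what does not change.** d2 − d1 equals the between-arm difference in the mean of each subject's own Study 2 minus Study 1 value; likewise d3 − d1. Every version below gives these same estimates.

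**Step 3: what does change.** A within-subject difference has variance 2σ²(1 − ρ), so the true variance of a contrast is

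2σ²(1 − ρ)(1/20 + 1/10) = 0.30σ²(1 − ρ).

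- *90 values treated as independent* uses 2σ² × 0.15 = 0.30σ². The standard error is too large by 1/√(1 − ρ): 1.41 times at ρ = 0.5 and 2.24 times at ρ = 0.8.
- *Placebo-mean-subtracted values, one-way ANOVA* uses 2σ²/20 = 0.10σ². The ratio to the true variance is 1/[3(1 − ρ)]: 0.33, 0.67 and 1.67 at ρ = 0, 0.5 and 0.8. It is too small below ρ = 2/3 and too large above.
- *Placebo-mean-subtracted values, repeated measures* uses 0.10σ²(1 − ρ). The standard error is √(0.05/0.15) = 0.577 of the true one at every ρ. For one contrast on 19 df, the critical value 2.093 acts as 0.577 × 2.093 = 1.208, giving a true error of 24.2%. At 2.5% per contrast it is 17.6%.

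**Step 4: simulated error of the overall test at nominal 5%** (60,000 null trials per setting)

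| Version | ρ = 0 | ρ = 0.5 | ρ = 0.8 |
|---|---|---|---|
| Drug-by-study interaction, subject error (2, 56 df) | about 5% | about 5% | about 5% |
| Two-way ANOVA, 90 values as independent | about 5% | 0.3% | about 0% |
| One-way ANOVA, placebo mean subtracted | 35% | 13% | 1% |
| Repeated-measures ANOVA, placebo mean subtracted | 35% | 35% | 35% |

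Conservatism has a price too. With drug effects of 1, 1 and 0 SD in Studies 1 to 3 and ρ = 0.5, power is 0.37 when the values are treated as independent, against 0.74 for the interaction with subject error.

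**Step 5: unequal spread.** With arms of 20 and 10, the pooled interaction test holds 5% only if the SDs are similar. It gives 9.8–10.1% if the placebo SD is 1.5 times the dapagliflozin SD, and 2.1–2.3% if it is 0.67 times. The documents favour neither direction. With placebo SD 0.67 to 1.5 times and Study 3 SD 1 to 2 times the others, Welch's test on the within-subject differences at 2.5% each kept familywise error between 4.5% and 5.3%. The pooled t-test ranged from 2.2% to 9.6%.

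**The case against.** The best defence is that the plan already describes a drug-by-study interaction in words. It defines a drug effect, compares it across three studies and interprets differences of it. No one could run the version with no error degrees of freedom, and a competent analyst would probably use a split-plot or mixed model. This stands in part: the aim is implied and the design supports a valid analysis. But an implied aim does not fix the error term, and the p-value depends on it.

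It is also fair that the 35% at every correlation needs two steps the plan does not mention, subtracting the placebo mean and using a within-subject error. One-way ANOVA on the same values is at least as close to the wording, and it runs from inflated to very conservative. A reader might infer that the sponsor has chosen an analysis with a 35% false-positive rate. The documents do not support that.

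A reader might also infer that assignment is redrawn for each study, because Study 3 repeats the ratio: "At 9AM, subjects will ingest dapagliflozin (10 mg) or placebo (2:1 randomization ratio"). That text restates the ratio in Item 2 and does not say that anyone is randomized again. The counts in Item 2 imply one assignment per subject, and nothing contradicts them.

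**Conclusion.** The point holds as a fault in the stated analysis, and should be fixed. The ANOVA cannot be run as written, and the computable forms closest to its wording misstate the error. Under the assumptions above, the overall error at a nominal 5% runs from near 0% to about 35%, against about 5% for the interaction with subject error. The 5% level, the SDs and the correlations are assumed, because the plan gives none. The point estimates are unaffected if data are complete and each subject keeps one assignment. It would go too far to say that the trial cannot answer its question: the design can, once the analysis is named.

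**What to change.** Replace the ANOVA sentence in Item 6 with one analysis:

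- For each subject, compute the differences in last-hour EGP, Study 2 minus Study 1 and Study 3 minus Study 1.
- Compare each difference between the dapagliflozin and placebo arms with Welch's t-test, which allows unequal variances with arms of 20 and 10. Take the reported p-value and interval from this test.
- Apply Bonferroni over these two contrasts: 2.5% each, with 97.5% intervals (for an assumed overall 5%, which the plan should state).
- Report the overall drug-by-study test, from a repeated-measures or mixed model with drug, study, drug-by-study and subject as the repeated unit, as supportive. Use that model as a sensitivity analysis if a subject misses a study.

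A line saying that each subject keeps one drug assignment in all three studies would help but is optional.

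The cost is rewording, with no new subjects, visits or assays. Intervals will be wider than a placebo-subtracted analysis would show. At ρ = 0.5 the pooled 97.5% half-width is 2.368 × √0.15 = 0.92 SD, against 2.433 × √0.05 = 0.54 SD. Welch averages 0.94 SD. The extra width is the uncertainty in the placebo mean, which the narrower interval leaves out.
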